#### **Primary:**

The proportion of patients who are in CR from Week 29 (Visit) to Week 37 (Visit) with a CS dose of  $\leq 10$  mg/day.

- A Cochran-Mantel-Haenszel (CMH) general association test stratified by disease type (PV or PF) and disease history (newly diagnosed or relapsing) will be used to compare rilzabrutinib with placebo. Newly diagnosed pemphigus is defined as patients diagnosed  $\leq 6$  months prior to Screening. Relapsing, chronic pemphigus is defined as patients diagnosed  $> 6$  months prior to Screening.

Patients who drop out of the trial, withdraw, or who receive a rituximab dose prior to Week 37 will count as non-responders in the analysis.

The primary efficacy analysis will be performed using a CMH general association test stratified by disease history (newly diagnosed or relapsing) to compare rilzabrutinib with placebo.

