### **2.3.2.2. Key Secondary Efficacy Endpoints**

The key secondary efficacy endpoints of this study include the following, ranked in order of importance:

1. Cumulative CS dose from Baseline to Week 37
2. Cumulative duration of CR with a CS dose  $\leq 10$  mg/day, from Baseline to Week 37
3. Time to first CR with a CS dose  $\leq 10$  mg/day CS, from Baseline to Week 37

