## 4. Statistical Analysis and Reporting

### 4.1. Introduction

Data processing, tabulation of descriptive statistics, calculation of inferential statistics, and graphical representations will be performed primarily using SAS (release 9.4 or higher). If the use of other software is warranted, the final statistical methodology report will detail what software was used for what purposes.

Continuous (quantitative) variable summaries will include the number of subjects ( $n$ ) with non-missing values, mean, standard deviation (SD), median, minimum, and maximum.

Categorical (qualitative) variable summaries will include the frequency and percentage of subjects who are in the particular category or each possible value.

Analyses will be presented by the treatment group assigned at randomization for the Blinded Treatment Period of the study and by double-blind treatment group and overall for the Open Label Phase and Long-Term Extension Phase of the study, unless stated otherwise.

The minimum and maximum will be reported with the same degree of precision (i.e., the same number of decimal places) as the observed data. Measures of location (mean and median) will be reported to 1 degree of precision more than the observed data and measures of spread (SD) will be reported to 2 degrees of precision more than the observed data.

Percentages will be presented to 1 decimal place, unless otherwise specified.

Unless otherwise indicated, all statistical tests will be conducted at the 0.05 significance level using 2-tailed tests, and  $P$  values will be reported. Corresponding 95% confidence intervals (CIs) will be presented for statistical tests.

Statistical testing will be performed at the 0.05 level using two-tailed tests.

To control for the overall type I error rate, hierarchical testing based on a fixed sequence procedure will be used. If statistical significance is declared for the primary analysis, formal hypothesis testing will be done for the key secondary endpoints in sequence until a non-significant result is reached. All other  $p$  values from key secondary and other secondary endpoints, after a non-significant  $p$  value is reached, will be considered nominal.

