##### **6.1.4. Multiple Comparisons**

The type I error rate of  $\alpha = 0.05$  will be maintained for the study by using sequential (hierarchical) testing for the primary and key secondary endpoints.

The testing will be done in the following order:

1. Primary endpoint based on PV patients in mITT population

2. Primary endpoint in mITT population (ie, PV+PF patients)
3. Key secondary endpoints based on PV patients in mITT population (in the order presented in Section 2.3.2.2)
4. Key secondary endpoints in mITT population (ie, PV+PF patients) (in the order presented in Section 2.3.2.2)

The study will be declared to be a positive study if the p-value for the primary endpoint based on PV patients in the mITT population is significant at two-sided  $\alpha = 0.05$  level. The test stops as soon as an endpoint is found not statistically significant at  $\alpha=0.05$  (2-sided). The nominal p-values for subsequent tests without adjustment will be provided in the summary tables for information purpose.

All other endpoints will be considered exploratory, and no adjustments will be made for multiple comparisons.

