### Time to event analyses:

For the analyses of following parameters,

- Time to first CR with a CS dose  $\leq 10$  mg/day CS, from Baseline to Week 37
- Time to first CR with a CS dose  $\leq 10$ mg/day, from Baseline to Week 61
- Time to initial flare/relapse from initial CDA to Week 37.

If a patient receives a rituximab therapy, the study data will be censored at the date of first rituximab administration for the above time to event analyses.

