**Table 4: Event and Censoring Details for Time to First CR with a CS dose at or below 10 mg/day**

Situation	Date of First CR/ Date of Censoring	Censored/ Event
No post baseline assessments	Date of first dose	Censored
Patient in CR status and with a CS dose of $\leq 10$ mg/day	First date that patient is in CR status and with a CS dose of $\leq 10$ mg/day as identified in Section 6.1.9.	Event
Rituximab administered	Date of first Rituximab administration	Censored
No CR with a CS dose of $\leq 10$ mg/day during the Blinded Treatment Period	Date of last efficacy assessment during blinded treatment phase (through Week 37)	Censored
Study discontinuation	Date of last efficacy assessment prior to or on the date of treatment discontinuation	Censored
Death before CR	Date of death	Censored

Note: Patients will be censored prior to a CR event at the earliest date of the censored events above should a censoring reason occur. Censoring reasons may be categorized for reporting (eg, by discontinuation reason).

- Three or more lesions within 1 month that do not heal spontaneously within 1 week or extension of established lesions = Yes if any of the following conditions are satisfied:
  - eCRF entry “Have new lesions appeared within a month that did not heal spontaneously within 1 week? OR Have there been extension of established lesions?” = Yes for any visits from Baseline up to Week 37.
  - At this visit, Has a Relapse occurred or is continuing?

The number of instances with investigator assessments of disease worsening will also be derived and categorized for reporting as 0, 1, 2, and  $\geq 3$ . After the first worsening, a patient can have additional worsening, but only after the patient returns to CDA first, and then the next worsening can happen.

- PDAI score  $< 3$  from Week 29 to Week 37 with a CS dose of  $\leq 10$  mg/day = Yes if the following conditions are both satisfied:
  - PDAI  $< 3$  = Yes for all visits from Week 29 through Week 37
  - Daily prednisone dose is  $\leq 10$  mg/day from Week 29 through Week 37 as defined in Section 6.1.9.
  - No Rituximab therapy prior to Week 37.

After applying the CS dose imputation as described in Section 6.1.5.2, a patient with partial missing data (missing PDAI assessment or CS dose) or complete missing data at any scheduled visit will be considered as a non-responder.

- Change from baseline = value at current time point – value at Baseline.

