## 8.2. Key Secondary Efficacy Analyses

The key secondary endpoint of Cumulative CS dose from baseline to Week 37, adjusted for time to study discontinuation will be calculated using the summation of the CS data as described in Section 6.1.9 and will be analyzed using an ANCOVA model with terms for treatment group and disease history. The estimated mean difference in cumulative CS usage (PRN1008 minus

placebo) and the associated 95% CI will be reported. Missing data for this endpoint is described in Section 6.1.5.2. The “time to study discontinuation” covariate is up to study discontinuation, first Rituximab administration if any, or the end of the blinded treatment period whichever happens first.

If outliers or skewed data is present, sensitivity analysis will be conducted on this secondary endpoint of average weekly CS usage over 36 weeks in which the data will be rank-transformed prior to analysis.

Cumulative CS dose from Week 37 to Week 61 will be analyzed similarly.

Cumulative duration of CR with CS dose  $\leq 10$ mg/day from Baseline to Week 37, will be based on a zero-inflated negative binomial model with terms for treatment group and disease history. The p-value and estimated treatment difference (parameter difference of PRN1008 minus placebo) from the negative binomial component will be reported, along with the 95% CI for the estimated parameter. The difference estimate will also be back-transformed (e.g. exponentiated) to demonstrate the relative difference in the number of pemphigus free days between treatment groups. Cumulative duration of CR with CS dose  $\leq 10$ mg/day from Baseline to Week 37 will also be summarized based on descriptive statistics.

A Kaplan Meier analysis will be used to estimate the median and other quartiles for Time (Days) to first CR with a dose of  $\leq 10$  mg/day, along with two-sided 95% confidence intervals. The number of events and censored observations will be presented as well as graphical representations of estimated survival curves. A hazard ratio for treatment comparisons will be presented, along with its 95% confidence interval, based on a Cox regression model with terms for treatment group and disease history. The endpoint will be evaluated based on a p-value from a log-rank test stratified by disease history for treatment group comparison. In addition, a landmark analysis will be done at Week 37 in the key secondary analysis and at Week 61 for the other secondary analysis.

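### Time to first CR censors deaths and failure-related withdrawals as if those patients could still reach CR, and no visible analysis tests that assumption

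*SAP*

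**What the plan says.** Time to first CR is the third of three key secondary endpoints, which SAP 2.3.2.2 lists "ranked in order of importance". SAP 6.1.4 puts it in the fixed sequence twice, and SAP 4.1 sets the level: "all statistical tests will be conducted at the 0.05 significance level using 2-tailed tests". SAP 8.2 names the test: "The endpoint will be evaluated based on a p-value from a log-rank test stratified by disease history for treatment group comparison".

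SAP Table 4 (section 6.1.8) defines the censoring:
- **Study discontinuation:** censored at "Date of last efficacy assessment prior to or on the date of treatment discontinuation". The row is headed by study discontinuation but dated by treatment discontinuation.
- **"Death before CR":** censored at the date of death.
- **Rituximab:** censored at first administration. SAP 6.1.5.2 repeats this: "the study data will be censored at the date of first rituximab administration for the above time to event analyses".

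For the primary endpoint, Protocol 9.3.5 says: "Patients who drop out of the trial, withdraw, or who receive a rituximab dose prior to Week 37 will count as non-responders". SAP 6.1.5.1 applies the same rule and adds a tipping-point analysis. Protocol 9.3.5 also classes need for rituximab as treatment failure for efficacy endpoints other than cumulative corticosteroid dose and the GTI composite. For the key secondaries it says further sensitivity analyses will be given in the SAP.

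**The concern.** CR is the favourable event. Log-rank, Kaplan-Meier and Cox methods need a censored patient to have the same future chance of CR as a patient still at risk. Someone who has died has none. Several exits in the protocol are treatment failures: severe and life-threatening pemphigus, Grade 4 related events and need for a further rituximab dose (7.2.1), need for other immunosuppressants (6.5.1), and potentially life-threatening worsening that stops study drug (Appendix 1). Other exits may have nothing to do with CR, such as a positive SARS-CoV-2 test in Germany (Appendix 10).

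If exits are selective and unequal, censoring removes likely failures from the denominator of the arm that loses more of them. More such exits on rilzabrutinib would favour rilzabrutinib; more on placebo would hide a real benefit. The visible SAP offers a Week 37 landmark analysis with no drop-out rule, subgroup analyses, and a supportive analysis with remote visits. None of these tests the assumption.

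**Working it through.** **Inputs from the documents.** About 60 patients per arm and at least 90 with PV, so about 45 per arm (Protocol synopsis); two-sided 0.05 (SAP 4.1); visits at Days 15 to 253 (SAP Table 2).

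**Inputs assumed, because the documents do not give them.** Drop-out by arm, the share reaching first CR by Week 37, and the timing of both.

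**Stated power.** The only power figure visible is for the primary endpoint, in the amendment history: 50% against 15%, at least 55 per group, more than 90%. With pooled p = 0.325 and n = 55, z = [0.35√55 − 1.96√(2 × 0.325 × 0.675)] / √(0.25 + 0.1275) = (2.596 − 1.298)/0.614 = 2.11, or 98.3%. At n = 45 it is 95.6%. The figure reproduces. No power or event count is visible for time to first CR.

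**Mechanism.** Suppose all drop-outs are patients who would not reach CR, and they leave before any CR occurs. Kaplan-Meier CR at Week 37 is then true CR / (1 − drop-out):
- Equal true CR of 35%, drop-out 25% vs 5%: 0.35/0.75 = 47% vs 0.35/0.95 = 37%. This is a false 10-point gap favouring the arm that lost more patients.
- True CR 50% vs 30%, drop-out 10% vs 25%: 0.50/0.90 = 56% vs 0.30/0.75 = 40%. The true 20-point gap shrinks to 16.

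If drop-out is unrelated to CR, censoring recovers 35% in both arms. Counting drop-outs as not in CR then gives 0.35 × 0.75 = 26% vs 0.35 × 0.95 = 33%, a false gap the other way.

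**Simulation, 60 per arm, unstratified log-rank, fully selective drop-out.** Early exit: withdrawals at Weeks 5-21, CR at Weeks 21-37. Spread: CR over Weeks 9-37, withdrawals over earlier visits.

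| Scenario | Early exit | Spread |
|---|---|---|
| Error favouring the arm with more drop-out (nominal 2.5%), CR 35% both, 25% vs 5% | 15.6% | 7.7% |
| Power under Table 4, CR 50% vs 30%, drop-out 10% vs 25% | 33% | 43% |
| Same, drop-outs kept at risk as not in CR | 58% | 59-60% |

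At 15% vs 5% drop-out, the one-direction error is about 4% to 6.5%. Timing matters as much as the drop-out gap. Late CR is plausible for patients on high starting doses: the 60 mg example in Protocol Table 6 needs four two-week steps and four weekly steps, 12 weeks from ECP, to reach 10 mg.

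**Simulation with the stratified test** (20,000 trials per cell, spread timing, assumed 60/40 disease-history split). Two-sided error under Table 4, fully selective drop-out:

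| True CR, n per arm | 15% vs 5% | 20% vs 5% | 25% vs 5% | 30% vs 5% |
|---|---|---|---|---|
| 50%, 60 | 7.0% | 9.6% | 14.0% | 20.9% |
| 50%, 45 (PV) | 6.7% | 8.6% | 11.7% | 17.0% |
| 30%, 60 | 5.8% | 7.1% | 8.5% | 10.5% |

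With half the drop-out selective (20-30% vs 5-10%, CR 50%), the error is 5.9-6.7%. With none selective it is 5.0-5.4%. For power in PV (45 per arm, CR 50% vs 25%, 5% drop-out on active), keeping drop-outs at risk gives about 68%. Table 4 gives 60%, 55%, 50% and 44% at placebo drop-out of 15%, 20%, 25% and 30%.

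**Place in the sequence.** Tests 1-2 are the primary endpoint in PV, then mITT. Tests 3-5 are the key secondaries in PV, and tests 6-8 the same in mITT. Time to first CR is tests 5 and 8.

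**The case against.** Four points on the other side have force.

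1. **Size.** The largest figures need a 20-point or greater gap in drop-out, all of it selective. At 15% vs 5%, or with half the drop-out selective, the excess is small. The documents cannot say which case applies.
2. **Gating.** A reader might infer that the trial's type I error rises to 15.6%. It does not: that is the local error of one test behind four others. If true CR were equal in both arms, the primary endpoint would usually fail first. The inflation matters only when the earlier hypotheses are false and pass while the first-CR null is true. Lost power is the more credible harm.
3. **Contradiction.** A reader might infer that Table 4 breaks a protocol rule on withdrawals. The non-responder sentence sits under the primary endpoint, and nothing extends its drop-out clause to this one; the protocol itself specifies Kaplan-Meier and log-rank here. The plan treats the same patient differently in two endpoints without saying why. Only the rituximab row meets a general protocol statement that points the other way.
4. **The obvious remedy.** A reader might infer that every withdrawal should be counted as not in CR in the main analysis. That is a choice of estimand. With unrelated drop-out of 25% vs 5%, it rejects a true null against the arm with more drop-out about 7-12% of the time. With true CR 50% vs 30% and 25% unrelated drop-out on drug, it can cut power from 52% to 19%.

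Two mitigations are partial. Table 4 allows censoring reasons to be tabulated, and part of SAP 6.1.5.1 is blacked out, so a further rule there cannot be excluded. Table 4 and 6.1.5.2 are nonetheless explicit.

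**Conclusion.** The concern stands for deaths and failure-related exits, and for the missing sensitivity analysis. Under fully selective, unequal drop-out (assumed 15-25% vs 5%, 60 per arm, true CR 35%), the one-direction error of this test is about 4% to 16% instead of 2.5%, depending on timing. With true CR 50% vs 30% and withdrawal of 10% vs 25%, power is about 33-43% instead of 60%. If drop-out is unrelated to CR, Table 4 holds its level, so it cannot be said that the arm with more withdrawals always gains. Deaths are likely few; withdrawals drive the effect. A false non-significant result at test 5 in PV would also block all three key secondary tests in mITT. The change should be made before unblinding.

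**What to change.** 1. **Main analysis.** In SAP Table 4, keep patients who die before CR, or who discontinue before CR for disease worsening, lack of effect or an adverse event, in the risk set as not in CR to the end of the blinded period (Day 253). Fix the mapping of recorded discontinuation reasons to these groups before unblinding, and state the estimand.
2. **Sensitivity analyses, same stratified log-rank test.** (a) All withdrawals counted as not in CR, matching the primary rule. (b) The present Table 4 censoring.
3. **Reconcile** the rituximab row of Table 4 and SAP 6.1.5.2 with the treatment-failure statement in Protocol 9.3.5, and make the heading and date of the discontinuation row refer to the same event.

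The cost is a few table rows and two extra runs. The main rule depends on how well the discontinuation reason is recorded, and it was not simulated separately; it matches the simulated keep-at-risk rule when every drop-out is failure-related and recorded as such. Counting withdrawals as not in CR works against the arm with more drop-out when drop-out is unrelated to CR, so the results under both rules should be reported.

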#### **Type of participant and disease characteristics**

- I01. Male or female patients, aged 18 to 80 years old with moderate to severe, newly diagnosed or relapsing PV or PF, with a clinical presentation and histopathology consistent with PV or PF (see [Section 8.4.3](#)).
- I02. Positive circulating anti-dsg1 or 3 autoantibody titer.
- I03. At Screening, PDAI score of at least 9 points for relapsing patients (diagnosed >6 months prior to Screening) or at least 15 points for newly diagnosed patients (diagnosed ≤6 months prior to Screening).
- I04. Adequate hematologic, hepatic, and renal function (including but not limited to absolute neutrophil count  $\geq 1.5 \times 10^9/L$ , hemoglobin [Hgb] >9 g/dL, platelet count  $\geq 100 \times 10^9/L$ , aspartate aminotransferase [AST] and/or alanine aminotransferase [ALT]  $\leq 1.5 \times$  upper limit of normal [ULN], albumin  $\geq 3$  g/dL, creatinine  $\leq 1.5 \times$  ULN).

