### **Other Secondary Endpoints**

- The proportion of patients who are in CR from Week 29 to Week 37 with a CS dose of  $\leq 5$  mg/day
- The proportion of patients who have a PDAI score  $< 3$  from Week 29 to Week 37 with a CS dose  $\leq 10$  mg/day
- Cumulative duration of CR with a CS dose  $\leq 10$  mg/day from Baseline to Weeks 61 and 109
- Cumulative duration of CR with a CS dose = 0 mg/day from Baseline to Weeks 61 and 109
- GTI score at Week 37
- Change in PDAI score from Baseline to Weeks 5, 13, 25, 37, 61, and 109
- Change in Autoimmune Bullous Disease Quality of Life (ABQOL) score from Baseline to Weeks 5, 13, 25, 37, 61, and 109
- Proportion of patients with ABQOL Score of zero at Weeks 5, 13, 25, 37, 61, and 109

- Change in EuroQOL-5 Dimension 5 Level (EQ-5D-5L) results (visual analog scale [VAS] results and individual dimension) scores from Baseline to Weeks 5, 13, 25, 37, 61, and 109
- Time to first CR with a CS dose  $\leq$ 10 mg/day, from Baseline to Weeks 61 and 109
- Total number of disease relapses/flares from initial CDA to Week 37
- Time to initial relapse/flare from initial CDA to Week 37
- Proportion of patients with 3 or more new lesions within 1 month that do not heal spontaneously within 1 week, or with extension of established lesions, from Baseline to Week 37
- Proportion of patients with at least one disease relapse/flare from initial control of disease activity (CDA) to Week 37
- Cumulative duration of CR with a CS dose  $\leq$ 10 mg/day, from Week 37 to Week 61
- Cumulative duration of CR with a CS dose = 0 mg/day, from Week 37 to Week 61

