### 1.3 SCHEDULE OF ACTIVITIES (SOA)

**Table 2: Schedule of Assessments - Blinded Treatment Period**

	Screening	Blinded Treatment Period												Early Termination (ET)	Unscheduled Visit
	Day -29) n,o WK (-4)	Day 1 Week 1 Pre-dose	Day 1 Week 1 Post-dose	WK 3	WK 5	WK 9	WK 13	WK 17	WK 21	WK 25	WK 29	WK 33	WK 37		
Visit Window				±3 days	±3 days	±3 days	±3 days	±3 days	±3 days	±3 days	±3 days	±3 days	±3 days		
Informed Consent	X														
Inclusion/Exclusion Criteria	X	X o													
Randomization		X													
Height	X														
Weight	X	X		X	X	X	X	X	X	X	X	X	X	X	X
Full physical examination	X														
Medical History	X														
Abbreviated physical examination		X		X	X	X	X	X	X	X	X	X	X	X	X
12-lead ECG	X														X
Vital Signs	X	X		X	X	X	X	X	X	X	X	X	X	X	X
Urinalysis b	X														X
Hep B and C, HIV, & QuantiFERON-TB Gold or Quantiferon-TB Gold Plus or TB-Spot	X														
Pregnancy test c	X	X			X	X	X	X	X	X	X	X	X	X	X
Skin biopsy d	X														
Hematology, coagulation, and serum chemistry e	X	X		X	X	X	X				X			X	X
HbA1c and LDL e (fasting)		X					X				X			X	X
FSH f	X														
PK sample		X	X g	X h	X h	X h	X h				X h			X h	X h
PD: anti-desmoglein-1 and -3 autoantibody titers by ELISA	X	X					X				X			X	X
PDAI	X	X		X	X	X	X	X	X	X	X	X	X	X	X
ABQOL, TABQOL	X	X		X	X		X				X			X	X

	Screening	Blinded Treatment Period												Early Termination (ET)	Unscheduled Visit		
	Day -29) n, o WK (-4)	Day 1 Week 1 Pre-dose	Day 1 Week 1 Post-dose	WK 3	WK 5	WK 9	WK 13	WK 17	WK 21	WK 25	WK 29	WK 33	WK 37				
Visit Window				±3 days	±3 days	±3 days	±3 days	±3 days	±3 days	±3 days	±3 days	±3 days	±3 days				
EQ-5D-5L	X	X		X	X		X			X			X		X		
GTI Index		X					X			X			X		X		
Efficacy Outcome Assessment i	X	X		X	X	X	X	X	X	X	X	X	X	X	X		
AEs m	X	X	X	X	X	X	X	X	X	X	X	X	X	X	X		
Concomitant medications	X	X		X	X	X	X	X	X	X	X	X	X	X	X		
Rilzabrutinib or placebo dispensed p		X			X	X	X	X	X	X	X	X	X		X		
CS daily dosing j	See Appendix 1														X	X	
Rituximab infusion k	See Appendix 1																
Photography l	X	X		X	X	X	X	X	X	X	X	X	X	X	X	X	
Drug reconciliation q (Rilzabrutinib or placebo /CS Dosing Documentation)		X		X	X	X	X	X	X	X	X	X	X	X	X	X	X

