## **6. General Issues for Statistical Analysis**

### **6.1. Statistical Definitions and Algorithms**

#### **6.1.1. Baseline Definitions**

Baseline values will be the last observation recorded prior to first dose of randomized treatment. Baseline value derivations will include evaluations specified to have been collected Pre-Dose on Day 1 as specified in study schedule. For patients from the ITT Population who are randomized but not treated, baseline will be based on their randomization date.

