#### **6.1.5.2. Imputation Procedures for Secondary Endpoints**

### Responder analyses:

If a patient received a rituximab dose prior to Week 37, the patient will be counted as a non-responder starting from the date of first dose of rituximab for following responder analyses:

- The proportion of patients who are in CR from Week 29 to Week 37 with a CS dose of  $\leq 5$  mg/day
- The proportion of patients who have a PDAI score  $< 3$  from Week 29 to Week 37 with a CS dose  $\leq 10$  mg/day

For the derivation of the following parameters:

- proportion of patients having three or more lesions within 1 month or extension of established lesions that do not heal within 1 week from Baseline to Week 37
- proportion of patients with at least one disease flare/relapse from initial control of disease activity (CDA) to Week 37,

A missing value will be considered as Yes with exception of the following:

- A 'No' can be inferred if adjacent visits are complete and reflect this same outcome. No more than one disease assessment can be imputed for this endpoint (i.e. this imputation is not applicable to consecutive missing visits). Note that, this imputation is not applicable at Week 37 when the study treatment a patient receives before and after the visit could be different.

If a patient received a rituximab dose prior to Week 37, the patient will be counted as Yes for the analyses of these two parameters.

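### The SAP rule for the three-or-more-new-lesions endpoint states no lesion count and, read literally, lets a pre-dose Baseline visit count as an event

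*SAP*

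**What the plan says.** - **Protocol, Section 1.1 (Other Secondary Endpoints) and Table 5.** The lesion-count part of the endpoint reads "Proportion of patients with 3 or more new lesions within 1 month that do not heal spontaneously within 1 week". The alternative event is extension of established lesions, and the window runs between Baseline and Week 37.
- **SAP Section 6.1.8, list after Table 4, label.** The variable is introduced as "Three or more lesions within 1 month that do not heal spontaneously within 1 week or extension of established lesions = Yes if any", followed by a list of conditions.
- **Same place, first condition.** An eCRF entry, shown in quotation marks, asks "Have new lesions appeared within a month that did not heal spontaneously within 1 week" and is joined by OR to a question on extension of established lesions. It counts when it is "Yes for any visits from Baseline up to Week 37".
- **Same place, second condition.** A relapse item, written with neither an answer value nor a visit window.
- **SAP Section 6.1.1.** "Baseline values will be the last observation recorded prior to first dose of randomized treatment".
- **Protocol Table 2.** The row "Efficacy Outcome Assessment" is marked at Screening, at Day 1 pre-dose and at ten visits from Week 3 to Week 37.
- **Protocol inclusion criterion I03.** "At Screening, PDAI score of at least 9 points for relapsing patients", and at least 15 points for newly diagnosed patients.
- **SAP Section 6.1.5.2.** "A missing value will be considered as Yes with exception of the following". The exception is a single missing visit whose neighbours are complete and show No; it does not apply at Week 37. Rituximab before Week 37 also counts as Yes.
- **SAP Table 6 and Section 8.3.** The endpoint is analysed like the primary, by a CMH test stratified by disease history, and sits outside the testing hierarchy.

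**The concern.** The label and the rule describe different events. The protocol asks for three or more new lesions. The rule as written is satisfied by any new lesion that fails to heal within a week. The relapse condition cannot restore the count, because meeting any one condition is enough.

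The visit window has a similar problem. Patients enter with active disease and the item looks back over a month, so a Yes on Day 1 before dosing is plausible. Treatment cannot change such an answer. Each one adds an event that carries no information on the drug and pulls the two arms together.

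At stake is a p-value reported under a three-or-more-lesions label for something else. The endpoint has some weight because the relapse endpoints exclude patients who never reach control of disease activity (SAP Section 6.1.8), whereas this one covers all patients from Baseline.

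**Working it through.** The documents give no event rate, effect size or power for this endpoint, so there is no planned figure to reproduce. The check is textual first; the arithmetic after it is illustrative.

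**1. Lesion count.** The protocol requires three or more new lesions. The SAP label keeps three but omits that the lesions must be new, as does the analysis paragraph in Protocol Section 9.3.6. The SAP's operative item has no number, and no other SAP section restores one. In addition, SAP Section 6.1.5.2 and Table 6 attach the non-healing requirement to extension of lesions, which the protocol endpoint does not.

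**2. Visit window.** The rule covers any visit from Baseline, Baseline is pre-dose, and the assessment is scheduled at Day 1 pre-dose. Nothing limits this rule to post-dose visits. The relapse variable in the same section, by contrast, counts only visits from control of disease activity onward.

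**3. What the count can change (assumed Poisson number of new non-healing lesions per month).**
- Mean 1: P(at least 1) = 1 − e⁻¹ = 63%; P(at least 3) = 1 − e⁻¹(1 + 1 + 1/2) = 8%.
- Mean 2: P(at least 1) = 1 − e⁻² = 86%; P(at least 3) = 1 − e⁻²(1 + 2 + 2) = 32%.

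**4. What the pre-dose visit can change.** Let a share q of each arm be Yes on Day 1. If that answer is independent of later events and of treatment effect, the observed rate is q + (1 − q)p and the arm difference shrinks by the factor (1 − q). Without independence, the difference lost is q × d, where d is the post-dose difference among the Day 1 Yes patients. If all of them would have an event later in both arms, d = 0 and nothing is lost.

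The table assumes independence, 60 per arm (Protocol Section 4.1), two-sided 0.05 and an unstratified two-proportion test. All rates are assumptions. Entries are observed rates in percent, placebo vs rilzabrutinib, with power in brackets.

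| Post-dose rates (q = 0) | q = 25% | q = 50% | q = 75% | q = 90% |
|---|---|---|---|---|
| 60 vs 35 (79%) | 70 vs 51.25 (56%) | 80 vs 67.5 (34%) | 90 vs 83.75 (17%) | 96 vs 93.5 (9%) |
| 50 vs 25 (82%) | 62.5 vs 43.75 (54%) | 75 vs 62.5 (31%) | 87.5 vs 81.25 (15%) | 95 vs 92.5 (8%) |
| 40 vs 20 (67%) | 55 vs 40 (38%) | 70 vs 60 (21%) | 85 vs 80 (11%) | 94 vs 92 (6%) |

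Worked cell (60 vs 35, q = 50%): 0.5 + 0.5 × 0.60 = 0.80 and 0.5 + 0.5 × 0.35 = 0.675. The difference is 0.125, half of 0.25. The pooled standard error is √(2 × 0.7375 × 0.2625 / 60) = 0.0803 and the unpooled one is √((0.16 + 0.2194) / 60) = 0.0795. So z = (0.125 − 1.96 × 0.0803) / 0.0795 = −0.41, and power is 34%.

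**The case against.** **The form is not in the documents.** The SAP runs two questions together inside one pair of quotation marks, so the text may be abridged, and the eCRF item may carry the count. This stands. A reader might infer that the trial is certain to measure a different outcome; the documents do not show that. They show that the SAP's rule, followed as written, does not contain the count.

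**From Baseline may mark only the start of follow-up.** The protocol uses the same window for this endpoint, and both documents use it for cumulative steroid dose and time to first remission. SAP Table 2 opens the blinded period with a post-dose Week 3 window and lists no Baseline visit. This is a fair reading of intent. But Table 2 governs analyses presented by study week, and the derivation neither refers to it nor excludes Day 1.

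**Saturation is not shown.** PDAI at Screening measures lesion burden; it does not show new or extending lesions on Day 1. Patients also start mandated steroids at Screening. A reader might infer that the endpoint will approach 100% in both arms, but no document gives a Day 1 Yes rate. The objection stands, and the table above is hypothetical.

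**The missing-data rule.** A reader might infer that most missing visits become Yes. The split between isolated and consecutive gaps is unknown, and scoring missing as an event is a disclosed choice. It adds Yes outcomes but is not a defect here.

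**Limited reach.** The SAP treats endpoints outside the hierarchy as exploratory. Randomisation balances pre-dose answers in expectation. The SAP also derives a number of worsening instances (0, 1, 2, 3 or more), which keeps some information, although it appears to rest on the same assessments. All of this limits severity; none of it corrects the rule.

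**Conclusion.** The point holds on the text. The rule states no lesion count and, read literally, admits a pre-dose visit. Single-lesion events and pre-treatment events can therefore be reported under a three-or-more label. The consequence is dilution and mislabelling of one other secondary endpoint, not bias toward either arm. The primary result, the key secondary tests and the family-wise error rate are unaffected.

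The size cannot be determined from the documents. The power figures depend on invented event rates, an invented Day 1 Yes share that is equal in both arms, and independence of the Day 1 answer from later events. If Day 1 Yes patients would mostly have a later event in both arms, the loss is smaller. Confidence is moderate, because the eCRF could show that the count is captured.

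**What to change.** In SAP Section 6.1.8:

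1. Derive the endpoint only from visits after the first dose of study drug through Week 37.
2. Check the eCRF. If it captures the count, state three or more new lesions in the rule. If it does not, rename the endpoint to any new non-healing lesion or extension of established lesions, and record this as a change from the protocol in SAP Section 10, which now says not applicable.
3. Complete the second condition: the relapse item equals Yes, in the same post-dose window.

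If the form holds the count, the cost is SAP wording and programming. If it does not, the cost also includes a documented departure from a protocol-defined endpoint.
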